TBI broadly affects the most diverse aspects of memory and presents a striking characteristic: the pattern of memory impairment is much more similar to that found in patients with frontal injury than individuals with amnesia [79]. In 2005, Mathias and Mansfield [80] compared 25 TBI victims with 25 healthy individuals matched for age and sex and found that the patients had worse performance in explicit memory. These same findings have been demonstrated in other studies, indicating memory disorders to be highly prevalent after DAI, affecting up to 40 to 60% of victims of severe TBI. In fact, TBI broadly affects the most diverse aspects of memory and presents a striking characteristic: the pattern of memory impairment is much more similar to that found in patients with frontal injury than individuals with amnesia [79].

Although the pathophysiological mechanism is not well understood, the cognitive changes found in these patients seem to be related to the impairment of circuits involving several neurotransmitters, such as serotonin, glutamate, dopamine, norepinephrine and acetylcholine [81]. In the acute phase of TBI there is a massive production and release of acetylcholine in combination with other neurotransmitters such as glutamate, catecholamines and serotonin, which contributes to the clinical disorders observed at this stage (changes in the level of consciousness, executive dysfunctions and memory impairment) [82, 83]. However, in chronic disorders affecting these cognitive domains, acetylcholine seems to be the most relevant neurotransmitter involved [81, 84]. After experimental studies demonstrated the impairment of cholinergic pathways after TBI in the 1990s, Dewar and Graham and Murdoch *et al.* [85, 86] conducted seminal studies *postmortem* in humans and demonstrated the pathophysiology of cholinergic dysfunctions observed in TBI victims. Despite the relative normalization of most neurotransmitters, cholinergic function remained chronically reduced, which was apparently directly related to the cognitive disorders observed [84-86].

The spontaneous cognitive recovery of DAI victims is well documented in the literature. Despite memory impairment after TBI, many patients have spontaneous recovery of cognitive functions. This is a well-known and reported phenomenon in the medical literature. Zaninotto *et al.*, [87] followed 18 patients with DAI for 12 months after trauma and documented a significant improvement in verbal fluency at the 12th

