The participants will be recruited when hospitalized at the Neurotraumatology Clinic of the Hospital das Clínicas Complex of the Medical School of the University of São Paulo (HCFMUSP). Overall admission and in-hospital records will be collected of each patient who meet the inclusion criteria. Patients will complete the minimum period of 6 months of TBI of follow-up.

In this study, REAC will be performed a single session of Neuro Postural Optimization (NPO), and 18 Neuro Psycho Physical Optimization – Brain Wave Optimization-G (NPPO-BWO-G) treatment sessions for 4 daily sessions. Each next of kin will receive written instructions with the date and time of the next sessions in order to avoid misunderstandings.

Search locations

The study will be conducted within the HCFMUSP, in São Paulo - SP, which has 2400 beds distributed among its 8 specialized institutes and 2 auxiliary hospitals (www.hc.fm.usp.br). The research locations in the various stages of the study are described in Table 6:

Table 6 - Stages of the study and the respective places where they will be carried out

Stage of the study	Location	Purpose
Patient selection	ICU - Neurotraumatology	
Electroencephalogram	ICU - Neurotraumatology	Brain waves mapping
Brain MRI	Central Institute	DAI diagnostic
REAC	ICU - Neurotraumatology	Intervention

DAI: diffuse axonal injury, ICU: intensive care unit, MRI: magnetic resonance imaging,

REAC: radio-electric asymmetric conveyer.

Study design

This is a prospective, randomized, double-blind, placebo-controlled clinical trial. According to the hypotheses of the present study, the sample size calculation was made considering an alpha error of 5% and based on other studies with similar design [135-140]. We estimate that 30 patients should complete the follow-up and be included in the statistical analyses. However, lack of adherence could be a problem. Thus, we estimate losses at 20% and calculated a final sample size of 36 participants. Subjects with no history of chronic neurological disorders will also be included and separated of DAI patients but submitted to the same protocols. After meeting the eligibility criteria, the participants will follow the steps of the study as described in Table 7.

Table 7 - The study steps

Patient selection	Medical record, radiology, participation consent
Step 1 (pre-intervention)	qEEG, TCD and brain4care up to 3 days before the start of REAC sessions
Step 2 (intervention)	NPO (single session)

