Step 3 (intervention)	NPPO-GW (18 sessions)
Step 4 (post-intervention)	qEEG up to 3 days after the end of REAC sessions

Follow-up discharge, 3m and 6m mRankin, GOSE, DASS 21

qEEG: quantitative electroencephalogram, TCD: transcranial Doppler, REAC: radio-electric asymmetric conveyer, NPO: neuro-postural optimization, NPPO-GW: gamma-waves neuro psycho physical optimization.

Randomization

A participant will select patients according to DAI criteria and obtain consent for participation with the next of kin for each eligible patient. Following, qEEG examinations will be performed. Up to three days after finishing NPPO-BWO sessions, a second acquisition of qEEG will be performed. All participants will be blinded between active and sham until the study is finished.

Participants will be randomly divided in a 1:1 ratio into two groups:

1. Active
2. *Sham*

The randomization process will be done in blocks interchanged, with the size of each block equal to four. The computerized system available in www.randomization.com will be used. For the persistence of allocation concealment, all evaluations will be performed using a database containing the group with a label "A" and "B". Consequently, all analyses were made without possible presumptions as to the allocation of the group.

Masking of Groups

In order to maintain masking in the study, the REAC device has a very similar shape, size, color, weight and emits very similar sounds. The participants and their families will not know which group the patient has been included up to the conclusion of the study. The entire process of selection, interview, neuropsychological evaluation and intervention with REAC will be similar in the groups, differing only the type of device used. The neuropsychologist responsible for the application of the neuropsychological tests will be unaware of the allocation of the intervention group.

Ethics

The project will be submitted to the Research Ethics Committee of the Hospital das Clínicas da Faculdade de Medicina da Universidade de São Paulo.

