The Kolmogorov-Smirnov test will be used to verify the parametric nature of the quantitative values observed in the battery of neuropsychological tests. The repeated measures related to the items neuropsychological assessment and cortical excitability will be compared through ANOVA-type analyses (*analysis of variance*) of two factors for repeated measures and the interaction test between the groups considered to test the null hypothesis[141, 142].

To compare the delta (Δ) values between the intervention groups, the Mann-Whitney test will be used. The comparison of the frequency of adverse effects according to the intervention groups will be performed using Pearson's chi-square. The Wilcoxon Rank-Sum test will be performed in the intra-group comparison regarding pre-intervention (E1) and post-early intervention (E2) performance in the neuropsychological assessment.

Statistically significant findings are those with a p-value or probability of type I error lower than 5%. The control of blinding will be done with the analysis of agreement with Cohen's kappa. The sample size is based on the TMT part B scores obtained after the intervention (E2). The analyses were performed using *Microsoft Excel* 2010 and *IBM SPSS (Statistical Package for Social Sciences)* v.21.0.

Funding

The present study will receive no funding. Device/software manufacturers will support the project providing their methods to be used in the study.

Chronogram

June 2024- Protocol submission.

Recruitment: One year.

Data analysis: Three months.

Publishing results: Manuscript submission to publication one month later.

References

1. Ghajar J. (2000) Traumatic brain injury. Lancet 356:923-929. [https://doi.org/10.1016/S0140-6736\(00\)02689-1](https://doi.org/10.1016/S0140-6736(00)02689-1)
2. Cole TB. (2004) Global road safety crisis remedy sought: 1.2 million killed, 50 million injured annually. JAMA 291:2531-2532. <https://doi.org/10.1001/jama.291.21.2531>

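### The within-group pre/post comparison of neuropsychological scores names the Wilcoxon rank-sum test, an independent-samples test, for paired data

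*Protocol*

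**What the plan says.** The protocol's Statistical analysis section assigns tests to three comparisons that matter here.

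- Longitudinal analysis: "The repeated measures related to the items neuropsychological assessment and cortical excitability will be compared through ANOVA-type analyses". This is a two-factor analysis, and its group interaction is the test of the null hypothesis.
- Change between arms: "To compare the delta (Δ) values between the intervention groups, the Mann-Whitney test will be used".
- Change within an arm: "The Wilcoxon Rank-Sum test will be performed in the intra-group comparison regarding pre-intervention (E1) and post-early intervention (E2) performance", on the neuropsychological assessment.

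The same section sets a general 5% significance threshold and does not exempt the within-arm comparison. The signed-rank test is not mentioned anywhere in the protocol.

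**The concern.** E1 and E2 are two measurements on one person. The rank-sum test compares two sets of different people and takes its null variance from that assumption. The protocol therefore gives one procedure, under two names, to two different designs: correctly to the between-arm changes, and incorrectly to the within-arm pre/post scores.

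If the two scores are positively correlated, the rank-sum test overstates the null variance, its p-values are too large, and a real within-arm change can be missed. If they were negatively correlated, the p-values would be too small. Because the general 5% rule applies, these p-values would be read as findings or as absence of findings. An analyst who ran the appropriate paired test instead would be departing from the written plan.

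**Working it through.** **Inputs from the protocol**

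- Completers (Study design): "We estimate that 30 patients should complete the follow-up and be included in the statistical analyses".
- Enrolled (Study design): "Thus, we estimate losses at 20% and calculated a final sample size of 36 participants". The figure is reproduced by 30 × 1.2 = 36. (Dividing by 0.8 would give 37.5, so 38; that is not the point here.)
- Allocation (Randomization): "Participants will be randomly divided in a 1:1 ratio into two groups". Pairs per arm are therefore 30 / 2 = 15, or 36 / 2 = 18 with no losses.
- Significance level: 5%. The protocol does not say one- or two-sided; two-sided is assumed.

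**Assumptions, because the protocol gives no values**

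- The E1–E2 correlation ρ ranges from −0.3 to 0.9.
- The within-arm shift is 0, 0.5 or 0.8 SD.
- Scores are bivariate normal with equal SDs.

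**Large-sample check.** With no true change, the actual variance of the rank-sum statistic is about (1 − ρ_s) times the variance the test assumes, where ρ_s is the Spearman correlation. For normal data ρ_s = (6/π)·arcsin(ρ/2). The true two-sided error at a nominal 5% is therefore 2·[1 − Φ(1.96 / √(1 − ρ_s))].

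For ρ = 0.5:

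- ρ_s = 1.910 × arcsin(0.25) = 0.483
- √(1 − 0.483) = 0.719
- 1.96 / 0.719 = 2.72
- true error = 0.64%

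The same formula gives 2.0% at ρ = 0.3, 0.05% at ρ = 0.7 and 8.4% at ρ = −0.3.

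**Simulation at the trial's size.** 20,000 data sets per setting, with both tests exact. Each cell is rank-sum / signed-rank, in per cent.

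15 pairs per arm:

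| ρ | Type I error | Power, 0.5 SD | Power, 0.8 SD |
|---|---|---|---|
| −0.3 | 7.7 / 4.7 | 27 / 19 | 52 / 41 |
| 0 | 4.7 / 4.9 | 24 / 24 | 53 / 52 |
| 0.3 | 2.0 / 4.6 | 20 / 32 | 53 / 66 |
| 0.5 | 0.8 / 4.5 | 18 / 42 | 54 / 80 |
| 0.7 | 0.2 / 4.8 | 14 / 62 | 56 / 95 |
| 0.9 | <0.01 / 4.9 | 10 / 98 | 61 / 100 |

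18 pairs per arm:

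| ρ | Type I error | Power, 0.5 SD | Power, 0.8 SD |
|---|---|---|---|
| −0.3 | 7.6 / 4.8 | 31 / 23 | 60 / 49 |
| 0 | 4.9 / 5.0 | 28 / 28 | 61 / 59 |
| 0.3 | 2.1 / 4.9 | 26 / 37 | 63 / 75 |
| 0.5 | 0.8 / 4.8 | 23 / 49 | 65 / 87 |
| 0.7 | 0.1 / 4.9 | 20 / 71 | 69 / 98 |
| 0.9 | <0.01 / 4.9 | 15 / 99 | 78 / 100 |

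The signed-rank test stays close to 5% at every correlation. The rank-sum test does so only at zero correlation. A separate run of 40,000 data sets for a larger shift of 1.0 SD, with 15 pairs and ρ = 0.3, gave 75% against 84%, so the gap narrows for large effects and weak correlation.

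**The case against.** **It is probably a label error.** Using two names in one section for what is a single test suggests that the authors had the paired Wilcoxon test in mind. That is likely, but the text as written still names the wrong test, and a prespecified plan should not need guessing.

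**The consequence is small.** With positive correlation the error is conservative. It touches neither the primary EEG comparison nor either between-arm analysis, and it cannot create a false claim of treatment effect. This stands, and it limits the weight of the point.

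**The power figures rest on assumed values.** Correlation, shift and normality are all assumed. The starkest contrast, 10% against 98%, needs a correlation of 0.9. This also stands, which is why the full range is shown. The pair counts are those of the DAI patients. The only cognitive goal listed under Goals concerns healthy volunteers, whose number is not given, and the text does not say which test serves that goal.

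**The measurements are not in the schedule.** Table 7 lists no neuropsychological battery before or after treatment. That is a separate gap; it does not make the named test suitable for the data the analysis section describes.

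**A descriptive label is unnecessary.** The interaction test already carries the null hypothesis, and the recovery studies cited in the protocol cover months. E1 to E2 appears to span little more than the treatment course: 18 sessions at up to four a day is at least five days. So those studies do not show recovery over this interval. The label is still consistent with the role given to the interaction test, and a change within one arm cannot separate treatment from other causes of change.

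**Conclusion.** The concern holds. The protocol fixes an independent-samples test for a paired comparison. With 15 pairs per arm and correlations of 0.3 to 0.7, the nominal 5% test has a true error of 2.0% down to 0.2%. Power for a 0.5 SD change is 20% to 14%, where the paired test has 32% to 62%. These figures depend on the assumed correlation, shift and normal scores. That the test does not match the design does not depend on them. The reach is limited to the supportive within-arm analysis of neuropsychological scores, so this is a definite error worth correcting, but not one that threatens the trial's main conclusion.

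**What to change.** In the Statistical analysis section, replace the test name, for example: *Within each group, E1 and E2 neuropsychological scores will be compared with the Wilcoxon signed-rank test; these within-group results are descriptive.* The descriptive clause keeps a within-arm change from being read as a treatment effect. The protocol itself notes that "The spontaneous cognitive recovery of DAI victims is well documented in the literature", and the between-group comparison is the one that answers the treatment question.

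The cost is one word for the test name and one added clause. Data, visits and sample size do not change.

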EFFECTS OF RADIO ELECTRIC ASYMMETRIC CONVEYER (REAC) NEUROBIOLOGICAL
TREATMENTS IN DIFFUSE AXONIAL INJURY: A RANDOMIZED, DOUBLE-BLIND CLINICAL
TRIAL

Unique Protocol Id: 84791824.8.0000.0068

Date: October/15/2025

Abstract

Background: Severe traumatic brain injury, particularly diffuse axonal injury (DAI), often leads to lasting neurological issues. Cerebral dysfunction in DAI can be evaluated by monitoring cerebral electrical activity (CEA) through EEG. The radio electric asymmetric conveyer (REAC) is a noninvasive method designed to rebalance cellular polarity via endogenous bioelectric fields and modulate CEA. This technique may alter CEA, which can be detected using quantitative EEG (qEEG).

Objective: To assess qEEG changes following DAI and brain wave alterations after a REAC protocol in this group.

Methods: In this prospective, randomized, double-blind clinical trial, adult (≥ 18 y.o.) DAI patients will be assigned to active or sham groups for 19 sessions of either true or sham REAC following ICU discharge. Interventions include one Neuro Postural Optimization session and 18 NPPO-BWO-G sessions (up to four per day). The main outcome is to evaluate changes in qEEG patterns through population brain electrical mapping after REAC therapies. Additionally, voluntary adults (≥ 18 y.o.) with no history of neurological diseases will be submitted to the same protocol to further comparisons between qEEG patterns.

Keywords: cognitive dysfunction; diffuse axonal injury; radio electric asymmetric conveyer; rehabilitation; traumatic brain injury.

LIST OF ACRONYMS AND ABBREVIATIONS

ANOVA.....	analysis of variance
ANP	neuropsychological assessment
BDNF.....	brain-derived neurotrophic factor
Beta-APP.....	Beta-Amyloid-Precursor-Protein
BVMT.....	Brief Visuospatial Memory Test
CE	cortical excitability
CRT	cognitive rehabilitation therapy
CONSORT	Consolidated Standards of Reporting Trials
cTBS.....	continuous theta burst stimulation
DAI.....	diffuse axonal injury
DWI	diffusion weighted imaging
EEG.....	electroencephalogram
EMP	motor evoked potential
FIC	intracortical facilitation
GABA	gamma-aminobutyric-acid
GRE.....	gradient echo
HVLT	Hopkins verbal learning test
LAT	traumatic axonal injury
LED	Light-Emitting Diode
LLLT	Low Level Light/Laser
LM	Resting Motor Threshold
LTD	Long-Term Depression
LTP.....	Long-Term Potentiation
M1.....	primary motor area

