MRI.....	magnetic resonance imaging
MSC	minimum state of consciousness
NMDA.....	N-Methyl-D-Aspartate
PDC.....	prefrontal dorsolateral cortex
PET	positron emission tomography

PVS	persistent vegetative state
RCT	randomized clinical trial
STAITER.....	state-trait anxiety inventory
SIII	short interval intracortical inhibition
TC	computed tomography
TBI	traumatic brain injury
TD	diffusion tensor
TF3D	three-dimensional fiber tractography
TMT	trail making test

LIST OF UNITS

µA	microAmpere
Cm	centimetre
Ms	millisecond
°C	degree Celsius
T	Tesla
Db	decibel
Mv	milliVolt
Hz	Hertz
V	Volt
m	meter

LIST OF FIGURES

Figure Y. Evaluations and interventions performed during the study.

Figure X CONSORT flow diagram

INTRODUCTION

Traumatic brain injury (TBI) is a leading cause of death and disability globally, significantly affecting the quality of life for patients and caregivers [1-3].

In the United States, traumatic brain injury is the leading cause of death for people aged 1 to 45 and a major risk factor for morbidity and mortality in polytrauma cases [4].

Although epidemiological data in Brazil are limited, studies indicate that TBI is a significant public health issue, primarily impacting the country's young and economically active population [5, 6].

Automobile accidents and falls are primary causes of traumatic brain injury, with incidence rates highest among young adults (20 to 29 years) and individuals over 80 years old [4-6].

TBI is a highly heterogeneous condition, with multiple classification systems that emphasize distinct aspects such as the underlying mechanism of injury, clinical severity, radiological characteristics, and pathophysiological processes. These classifications play an important role in standardizing data collection, identifying prognostic factors, and informing the selection of appropriate therapeutic approaches tailored to individual cases.

From a pathophysiological perspective, traumatic brain injury (TBI) causes damage through primary lesions—direct energy transfer to the brain at trauma—and secondary effects, which involve cellular and molecular changes occurring for hours to weeks post-injury [7, 8].

Diffuse axonal injury (DAI) is a type of lesion in TBI that leads to significant brain dysfunction and affects roughly 40% of patients, making it a leading cause of neurological problems in survivors [9-11].

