Given the significant brain damage and multiple disabling neurological sequelae, in severe TBI patients, combined with the limited efficacy of conventional pharmacological and cognitive rehabilitation interventions, REAC may be a promising therapeutic approach for affected patients. We will conduct a randomized clinical trial to assess REAC's effects in patients with DAI.

GOALS

Primary Endpoint

- To evaluate the qEEG changes in patients with subacute/chronic DAI, following REAC neuromodulation.

Secondary Endpoint

- To evaluate the qEEG changes in adults free of neurological conditions, following REAC neuromodulation.
- To evaluate cognitive and humor changes in adults free of neurological conditions, following REAC neuromodulation.

LITERATURE REVIEW

TBI Classifications

TBI is typically a heterogeneous condition being classified by clinical severity, mechanism of injury and pathophysiology, all of which are relevant to properly determine treatment and prognosis.

From a clinical point of view, TBI is classified as mild, moderate and severe depending on the duration of the loss of consciousness, level of consciousness on the Glasgow Coma scale and the presence or absence of post-traumatic amnesia, as well as its duration. However, knowledge of other information, such as history of exogenous intoxication, use of sedatives and neuromuscular blockers, as well as orotracheal intubation, is essential to avoid misclassification of TBI [41, 42].

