Patients will be submitted qEEG testing before starting the REAC protocols and then after finishing the last session. For data collection, EEG examinations were performed using an international 10-20 electrode placement system. The examination will last 30 minutes, 15 minutes with eyes open and 15 minutes with eyes closed (relaxed wakefulness. The digital 19-channel Nihon Kohden® EEG 1200 version 01.71 (Nihon Kohden, Tokyo, Japan) will be used., The channels follow the 10-20 system: seven located in the frontal lobe (Fz, Fp1, Fp2, F3, F4, F7 and F8), three in the center (Cz, C3 and C4), four in the temporal lobe (T3, T4, T5 and T6), three in the parietal lobe (Pz, P3 and P4) and two in the occipital lobe (O1 and O2). For quantitative analysis, the data were converted using the Neuromap of the Neuroworkbench software, transferred to Matlab vR2002b and treated with the EEGLab v2023.0116 software. After being imported into EEGLAB, the spatial coordinates of each electrode will be inserted according to the 10-20 system. The signals were referenced using the average between the channels. The baseline was automatically removed using a 0.5Hz 117 high-pass filter. Artifacts are automatically rejected and incorrect data periods removed. Finally, the Independent Component Analysis is performed.

Processing

Using EEGLab's Darbeliai tool, the power spectral density of each channel is calculated for four bands: delta (1-4 Hz), theta (4-8 Hz), alpha (8-13 Hz), beta (13-32 Hz), in which the absolute power will be determined. The relative power analysis will be performed using the Fast Fourier Transform FFT.

OUTCOMES

Primary:

Observe if there are significant changes in the electroencephalographic pattern, compared between the groups.

Secondary:

Observe if there are:

Significant clinical improvement determined by the mRankin and GOSE scales between the groups.

Statistical analysis

Categorical variables will be presented in absolute values and relative frequencies, while continuous variables will be described in measures of central tendency and dispersion. All analyses will be performed under the intention to treat.

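### The only variable named as the basis of the sample size is TMT part B, but the primary outcome is the between-group qEEG change, so 30/36 has no stated basis in the primary

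*Protocol*

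**What the plan says.** **Sizing variable.** Protocol, Statistical analysis: "The sample size is based on the TMT part B scores obtained after the intervention (E2"). The abbreviation list expands TMT as "trail making test"; the test is named nowhere else.

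**Primary.** Three places agree that it is qEEG:
- Abstract: "The main outcome is to evaluate changes in qEEG patterns through population brain electrical mapping after REAC therapies".
- Goals: "To evaluate the qEEG changes in patients with subacute/chronic DAI, following REAC neuromodulation".
- Outcomes: "Observe if there are significant changes in the electroencephalographic pattern, compared between the groups".

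**Other outcomes and assessments.** The secondary outcomes are the mRankin and GOSE scales. Table 7 lists qEEG, TCD and brain4care before treatment, qEEG after it, and mRankin, GOSE and DASS 21 at discharge, 3 and 6 months. The one cognitive goal concerns adults free of neurological conditions and names no test.

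**Sizing text.** Study design says the calculation follows the trial's hypotheses, uses a 5% alpha and is "based on other studies with similar design [135-140"]. It then gives 30 patients completing follow-up, a 20% loss and a final 36.

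**The concern.** A sample size answers a question about one variable. Here the only variable named is a cognitive score that the protocol makes neither primary nor secondary and does not place in its table of study steps. A reader, ethics committee or journal cannot tell what qEEG difference, if any, the trial was planned to detect, and could not judge a null qEEG result against the design. At stake is the stated rationale for N. Randomisation, assessments and tests are unaffected.

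**Working it through.** **1. Where TMT part B stands.**

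| Place in the protocol | TMT part B | qEEG |
|---|---|---|
| Abstract, main outcome | no | yes |
| Goals | no | primary |
| Outcomes | no | primary, between groups |
| Table 7 | no | before and after treatment |
| Study design, sizing sentences | no | no |
| Statistical analysis, sizing sentence | yes, at E2 | no |

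**2. Can the 30 be reproduced?** No. A two-group calculation needs alpha, sidedness, power, a difference and an SD. Only alpha (5%) is given. References 135-140 are, by their titles, brain or magnetic stimulation studies in Alzheimer's disease. Several titles name cognitive or language measures; none names TMT or qEEG.

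**3. Can the 36 be reproduced?** Yes, by adding 20% to the completers: 30 x 1.2 = 36. A 20% loss, however, applies to those enrolled:
- expected completers: 36 x (1 - 0.20) = 28.8, about 29, or 14.4 per arm;
- shortfall against the stated 30: 30 - 28.8 = 1.2;
- enrolment that would leave 30: 30 / 0.80 = 37.5, rounded up to 38;
- loss implied by going from 36 to 30: 6/36 = 16.7%.

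**4. What could these numbers detect? (illustration only)** These assumptions are not in the protocol: one measure, two-sided 5%, 80% power, normal data, and a difference d in SDs of the analysed change.

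Normal approximation: d = (1.960 + 0.842) x sqrt(2/n), with n per arm. The t-test values solve the noncentral t. The Mann-Whitney values divide the t-test values by sqrt(0.955), the asymptotic efficiency under normality.

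| n per arm | Normal approx. | t-test | Mann-Whitney |
|---|---|---|---|
| 18 (all 36 measured) | 0.934 | 0.961 | 0.984 |
| 15 (30 completers) | 1.023 | 1.060 | 1.084 |
| 14 (about 29 completers) | 1.059 | 1.100 | 1.126 |

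In simulation with exact critical values, Mann-Whitney power at the last column's differences was 0.790, 0.784 and 0.795. Those differences are therefore slightly optimistic, and roughly 1 SD is as precise a statement as the material supports.

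For scale, t-test power with 15 per arm is 26% at an assumed d of 0.5, 56% at 0.8, 75% at 1.0 and 89% at 1.2.

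**5. Limit of the illustration.** The Processing text says "the power spectral density of each channel is calculated for four bands". With 19 channels that is 19 x 4 = 76 values, before eye condition and absolute or relative power. The figures in step 4 apply to one measure, not to a search across 76.

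**The case against.** **TMT part B may well be collected.** Masking of Groups describes a blinded neuropsychologist giving tests. Statistical analysis gives the neuropsychological assessment two time points, E1 before and E2 after the intervention, and the TMT sentence uses E2. This stands as far as it goes: a reader might infer that TMT part B is never measured, and the documents do not support that. What they support is that it is absent from Goals, Outcomes and Table 7. Even if collected, it would not be the primary.

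**The two sizing statements may describe one calculation.** Some of the cited studies used cognitive or language measures, judging by their titles, so a TMT calculation could have drawn on them. The two statements are unreconciled rather than contradictory. The real mismatch is between the sizing variable and the primary.

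**The missing inputs may be in a statistical analysis plan.** They may be, and their absence alone would not be a finding. The point rests on what the protocol itself states: a sizing basis that is not its primary, and an N presented as calculated for its hypotheses.

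**The Mann-Whitney figures presuppose a test.** This is correct. The protocol says that for delta "values between the intervention groups, the Mann-Whitney test will be used", but does not say which variable's deltas; the surrounding sentences concern neuropsychological assessment and cortical excitability. No sentence there assigns a test to qEEG.

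**Attrition is trivial.** The gap is 1.2 expected completers, and adding 20% is common practice. It is minor, but the printed figures do not agree and the correction is one line.

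**Conclusion.** The point holds as a defect of rationale. The sizing sentence names a variable that is not this trial's primary, and nothing else in the protocol ties 30 or 36 to the qEEG comparison.

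A reader might go further and infer that the trial is underpowered. The documents do not support that. They give no qEEG effect or SD, so adequacy cannot be judged either way. On the assumptions in the working, 15 to 18 per arm would detect a difference of roughly 1 SD on one measure. Whether that is realistic for qEEG is unknown from this text.

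The attrition discrepancy rests only on the protocol's own figures: about 29 expected completers against a stated 30. Which qEEG measure should be primary is a separate question of endpoint definition and need not be settled to correct this error.

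**What to change.** Keep N = 36 and change the wording in three places.

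1. Delete the TMT part B sentence, or reconcile it with Study design, Outcomes and Table 7, so that the protocol states one basis for the sample size.
2. Justify N for the qEEG primary, giving the inputs used, or state that 36 is a feasibility number not powered for that outcome. If a detectable difference is quoted, label it as an illustration and list its assumptions: one measure, two-sided 5%, 80% power, number per arm, and the test assumed.
3. Restate the attrition line as about 29 expected completers from 36 at 20% loss.

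Deleting the TMT sentence adds no patients or assessments. If the authors instead keep TMT part B and enter it in Table 7, that could add an assessment. The main cost is that the stated rationale becomes less favourable: the protocol would show a qEEG-based justification that can be questioned, or admit that N was not derived from the primary.
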